CONCLUSION: The Erchonia® HLS Laser is an effective tool for improving irritability and the presentation of other symptoms and behaviors associated with autistic disorder in children and adolescents, with positive changes maintained and augmented over time, including a six-month follow-up period during which time no procedure administration occurred.

STUDY RATIONALE

Considering the positive outcomes of the prior feasibility and clinical studies, it is determined that application of the Erchonia® HLS may provide a simple, non-invasive, safe, effective and side-effect free alternative therapy to reduce the severity of irritability symptoms and behaviors of autistic disorder in children. The currently proposed full-scale controlled pivotal trial is intended to demonstrate this to a statistically significant and clinically meaningful extent.

STUDY DESIGN

This clinical study is a double-blind, placebo-controlled randomized parallel group design.

TREATMENT GROUPS

Each subject is randomized to the test treatment group or to the placebo treatment group, as follows:

- ➤ Test Group: Subjects randomized to the test group will receive the study treatments with the active (true) Erchonia® HLS device.
- ➤ Placebo Group: Subjects randomized to the placebo group will receive the study treatments with the 'fake' (placebo) Erchonia® HLS device.

DOUBLE BLIND DESIGN

This clinical study will be a double-blind design, such that neither the subject nor the investigator will be aware of whether a subject has been assigned to the test group or to the control group until after the study is complete.

Maintenance of study double-blind throughout the study duration will be achieved as follows:

- 1) Each subject will be randomly assigned to Treatment Group A or to Treatment Group B. Subjects assigned to Treatment Group A will be treated with the Erchonia® HLS A and subjects assigned to Treatment Group B will be treated with Erchonia® HLS B. Only the study Sponsor will know which label ('A' or 'B') corresponds to the actual (test) HLS device and which label corresponds to the 'fake' device until the final study data analysis is complete. The Sponsor will ensure that this information is stored and maintained confidentially at the Sponsor's work site. This knowledge will not be shared with the investigators, the subjects, or the study Monitor until the final data analysis is complete.

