Therefore, the clinically significant effect size of the Erchonia® HLS Laser Device as applied to children and adolescents with autistic disorder in the proposed clinical study based on prior experience and research is defined as a minimum mean difference of -8.5 points on the ABC Irritability Subscale score from baseline to endpoint (week four) between active and placebo treatment groups.

SECONDARY EFFICACY OUTCOME MEASURES

The following secondary efficacy outcome measures will be evaluated in this study:

- ➤ Positive Response Rate: Difference in Positive Response Rate between treatment groups, where 'Positive Response Rate' is defined as satisfaction of both of the following 2 criteria:
 - ✓ >= 25% reduction from baseline to endpoint in the Aberrant Behavior Checklist (ABC) Irritability Subscale score based on the subject's primary caregiver's rating; AND
 - ✓ Clinical Global Impressions Improvement (CGI-I) scale rating of 1 or 2 (much improved or very much improved) at study endpoint as determined by the clinician's evaluation
- ➤ Mean change from baseline to endpoint in the other 4 ABC Subscale scores, based on ratings by the subject's primary caregiver:
 - ✓ Letharqy/Social Withdrawal
 - ✓ Stereotypic Behavior
 - √ Hyperactivity/Noncompliance
 - ✓ Inappropriate Speech
- ➤ Mean change from baseline to endpoint in the global ABC score
- ➤ Change in ratings on the CGI-S from baseline to study endpoint evaluation
- ➤ Change in ratings on the CGI-I from baseline to study endpoint evaluation
- Caregiver Satisfaction with Study Outcome ratings between treatment groups and across evaluations

STATISTICAL METHODS

Efficacy analysis will be according to the intent to treat (ITT) principle by last observation carried forward (LOCF).

Intent to Treat: Subjects will be included in the ITT analysis if they complete their baseline clinical assessments and had at least one post-randomization efficacy evaluation and corresponding baseline value.

Last observation carried forward (LOCF): Missing data will be handled by carrying forward the last observation for the relevant measure. The LOCF data set included date recorded at a given time point, or, if no observation was recorded at that time point, data carried forward from the previous time point with available data. Baseline data will not be carried forward or averaged to impute missing values for the LOCF data set.

STATISTICAL ANALYSIS

Primary Efficacy Analysis

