For the continuous primary efficacy measure of ABC Irritability Subscale score, change scores will be evaluated by analysis of covariance (ANCOVA). The ANCOVA models for LOCF data sets will include the baseline measure as a covariate and treatment (active of placebo) as main effects.

Secondary Measures Analysis

- ➤ For the continuous secondary efficacy measures of the other 4 ABC Subscale scores, and the Global Score, change scores will be evaluated by analysis of covariance (ANCOVA). The ANCOVA models for LOCF data sets will include the baseline measure as a covariate and treatment (active of placebo) as main effects. A two-way significance level of 5% will be considered statistically significant.
- ➤ The categorical measures of the CGI will be analyzed within the framework of the generalized Cochran-Mantel Haenszel (CMH) procedure.
- Responder rate will be evaluated using Fisher's exact test to compare the proportion of responder rates between the test and control groups.

P-values will be 2-tailed tests of significance rounded to 3 decimal places. All analyses will be performed at the 5% significance level.

CAREGIVER SATISFACTION

Caregiver satisfaction ratings will be descriptively presented through the number and percentage of responses per response category. Fischer's Exact Test will be employed to determine the significance of the difference in categorical responses between treatment groups.

BLINDING EFFICACY EVALUATION

Blinding efficacy evaluation will be conducted through analysis of findings from the Caregiver and the Assessment Investigator Perceived Subject Group Allocation and Rationale responses, recorded at completion of the procedure administration phase (study endpoint).

Statistical evaluation of blinding efficacy will be performed as follows:

- (i) The percentage of caregivers who correctly perceived the subject's procedure group assignment and the percentage of caregivers who did not correctly perceive the subject's procedure group assignment will be calculated.
- (ii) The percentage of times the assessment investigators correctly perceived subjects' procedure group assignment and the percentage of times the assessment investigators did not correctly perceive subjects' procedure group assignment will be calculated.

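### Nine secondary efficacy comparisons are each called significant at two-sided 5%, with no adjustment, no order and no condition that the primary succeeds first

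*Combined protocol and SAP*

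**What the plan says.** The section on secondary efficacy outcome measures opens with "The following secondary efficacy outcome measures will be evaluated in this study" and lists:

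- Positive Response Rate (1)
- "Mean change from baseline to endpoint in the other 4 ABC Subscale scores" (4)
- "Mean change from baseline to endpoint in the global ABC score" (1)
- change in CGI-S (1)
- change in CGI-I (1)
- caregiver satisfaction (1)

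That makes nine between-group comparisons. The Statistical Analysis section assigns a test to each: ANCOVA for the ABC scores, Cochran-Mantel-Haenszel for the CGI scales and Fisher's exact for response. The Caregiver Satisfaction section adds a Fisher's exact test for satisfaction. For the ABC secondaries the plan says "A two-way significance level of 5% will be considered statistically significant". It then sets the rule for everything: "P-values will be 2-tailed tests of significance rounded to 3 decimal places" and "All analyses will be performed at the 5% significance level".

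The opening of the Statistical Analysis Plan ties study success to the primary endpoint alone, on the ITT-LOCF analysis at 0.05. The Indication for Use section names irritability only.

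**The concern.** Tying study success to the primary does not stop a secondary result from being called statistically significant. Under the plan's own wording, a secondary p-value of 0.04 would carry that label even if the primary failed. With nine chances at 5%, the probability that at least one crosses the line by chance is well above 5%.

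This matters because the plan never calls the secondaries exploratory, and the sponsor has made broad efficacy statements before. The conclusion of the earlier randomised study says that the device "is an effective tool for improving irritability and the presentation of other symptoms and behaviors associated with autistic disorder in children and adolescents". A similar statement after this trial, which is to support a de novo application, could rest on secondary p-values with no error control behind them.

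**Working it through.** The documents give no familywise error rate for the secondaries, so there is no stated figure to reproduce.

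**Inputs.** Nine two-sided tests at 0.05 (Secondary Efficacy Outcome Measures; Statistical Analysis). The correlation between secondary endpoints is not stated and has to be assumed. Table 1 of the feasibility study allows an indirect estimate, because it gives SDs for the five ABC subscales and for the global score, which is their sum.

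**Step 1: ceiling under independence.** 1 − 0.95^9 = 0.370, or 37%.

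**Step 2: correlation implied by Table 1.** For a sum of scores with SDs s_i and total SD g, a single common correlation consistent with the variances is r = (g² − Σs_i²) / ((Σs_i)² − Σs_i²).

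- Change: g = 25.84, Σs_i = 27.81, Σs_i² = 184.52. r = (667.71 − 184.52) / (773.40 − 184.52) = 483.18 / 588.87 = 0.82.
- Baseline: g = 31.56, Σs_i = 35.84, Σs_i² = 298.90. r = (996.03 − 298.90) / (1284.51 − 298.90) = 697.13 / 985.61 = 0.71.
- Endpoint: g = 19.22, Σs_i = 21.79, Σs_i² = 114.16. r = (369.41 − 114.16) / (474.80 − 114.16) = 255.25 / 360.64 = 0.71.

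**Step 3: familywise error under correlation.** Take nine normal test statistics with common correlation r, each tested two-sided at 5%. The last column counts only results in the device's favour (2.5% upper tail each).

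| Common r | At least one false result | At least one favouring the device |
|---|---|---|
| 0 | 37.0% | 20% (1 − 0.975^9 = 0.204) |
| 0.3 | 32.6% | 17% |
| 0.5 | 26.9% | 13% |
| 0.7 | 20.2% | 10% |
| 0.82 | 15.8% | 8% |

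**Step 4: check with tests close to those planned.** A null simulation used 20 per arm and 6,000 runs per correlation. T-tests stood in for ANCOVA, the global score was the sum of the subscales, and response was built from irritability and CGI-I. A mean-score CMH test was used for the CGI, and Fisher's exact for response and satisfaction; category cut-points were assumed. The chance of at least one false result was 31% at r = 0, 28% at 0.3, 23% at 0.5, 18% at 0.7 and 16% at 0.82. The two Fisher tests ran at about 2% actual size, which pulls the figures down.

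**Step 5: effect of a gate.** In the same simulation, requiring a significant primary first cut the chance of any false secondary claim to between 2.3% (r = 0) and 4.6% (r = 0.82). By construction it cannot exceed 5% when the device has no effect on any endpoint.

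**The case against.** The strongest reply is that the secondaries are supportive only. Study success depends on the primary and the indication is irritability alone, so no proposed label claim needs a secondary. The family is finite and prespecified and p-values are reported to three decimals, so a reader could apply Bonferroni (0.05/9 = 0.0056) or Holm unaided. All of that stands and limits the consequence. It does not remove the point, because the plan itself attaches the words statistically significant to each comparison without condition.

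A reader might infer that the false-positive chance is a flat 37%, or 20–37%. The documents do not support that. Independence is ruled out by the endpoints' construction: the global score sums the subscales, including the 15 irritability items, and Positive Response contains CGI-I. Table 1 points to the low end, and only about half of the false results would favour the device.

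A reader might also infer that missing adjustment produced an unsound claim after the earlier trial. That is not supported either. Its primary was reported at p<0.0001, as were the responder and ABC comparisons, so a gate would have been passed and Holm would not have removed those results. The episode shows that the sponsor makes broad statements from secondary measures, not that multiplicity made one false.

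Finally, it would be too strong to say that a regulator could rely on no secondary result at all; very small p-values would survive adjustment.

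**Conclusion.** The point holds in limited form. Nine secondary comparisons are each labelled significant at two-sided 5% without adjustment, order or gate. If the device does nothing, the chance of at least one false secondary result is roughly 16–20% at correlations of 0.7 to 0.82, with a ceiling of 37% under independence; in the device's favour it is about 8–10%, with a ceiling of 20%.

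The lower range assumes one common correlation for all nine endpoints, taken from ABC SDs in 11 open-label subjects. CGI and satisfaction ratings could be less correlated, which would raise it. The count of nine assumes that satisfaction is tested once; separate tests at weeks 4 and 8 would make ten (40% if independent, 21% at 0.7).

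Type I error for study success and the irritability indication are unaffected. What lacks protection is any efficacy statement that rests on a secondary measure, above all one made after a failed primary. This is a cheap improvement worth making, not a flaw in the primary analysis.

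**What to change.** In the Statistical Analysis section, replace both "All analyses will be performed at the 5% significance level" and "A two-way significance level of 5% will be considered statistically significant" with one rule:

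1. Secondary measures are formally tested only if the ITT-LOCF primary test is significant at 0.05.
2. If so, the family of seven (Positive Response Rate, CGI-I, CGI-S and the four other ABC subscales) is tested by Holm's method at an overall two-sided 5%. Alternatively, the sponsor writes out a fixed order in full before unblinding, including the order of the four subscales, and testing stops at the first non-significant result. The gate on the primary applies either way.
3. The ABC global score, which partly retests the primary, and caregiver satisfaction are reported with estimates and 95% intervals and no significance claim. The Fisher test sentence in the Caregiver Satisfaction section is amended to match.

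The primary's 0.05 level remains defined at the start of the Statistical Analysis Plan, so removing the general sentence leaves no gap there.

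Cost: a few sentences, settled before unblinding. Some secondary comparisons lose a formal significance claim. The primary test, its power and the sample size are unchanged.

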STUDY EVALUATIONS: All subjects were evaluated using the Aberrant Behavior Checklist (ABC) Global Scale and 5 Subscales (Irritability/Agitation, Lethargy/Social Withdrawal; Stereotypic Behavior; Hyperactivity/ Noncompliance and Inappropriate Speech); and the Clinical Global Impressions Severity of Illness (CGI-S) and Improvement/Change (CGI-C) scales at baseline, week 2 (interim), week 4(endpoint) and week 8 (post-procedure) of the study. Test group subjects were additionally evaluated at 6 months post-procedure.

STUDY RESULTS

Primary Outcome Measure: Primary outcome measure was predefined as the mean change from baseline to endpoint in the Aberrant Behavior Checklist (ABC) Irritability & Agitation Subscale score. Primary efficacy study success was pre-established as the detection of a minimum mean difference of -8.5 points between test and placebo groups in the baseline to endpoint change in ABC Irritability Subscale score adjusted for baseline ABC Irritability Subscale score.

The adjusted mean difference in the baseline to study endpoint change in the ABC Irritability Subscale score between all 40 active procedure subjects and placebo subjects was -13.82 in favor of the active procedure group, notably greater than the preestablished study success criteria of a -8.5-point difference. ANCOVA analysis found this difference to be statistically significant at p<0.0001 (F=30.07), independent of baseline ABC Irritability Subscale score.

ABC	Combined (n=401)		Test (n=21)		Cross-Over (n=19)		Placebo	o (n=19)
Irritability	Mean	SD	Mean	SD	Mean	SD	Mean	SD
Baseline	30.45	6.74	30.52	6.73	30.37	6.94	29.58	6.83
Endpoint	16.90	9.05	15.71	9.94	18.21	8.02	29.89	6.55

Change -13.55 6.387	-14.81	6.40	-12.16	6.21	0.32	1.38
---------------------	--------	------	--------	------	------	------

The table below show the mean and standard deviation and the magnitude of change in ABC Irritability Subscale scores from baseline to endpoint.

Positive Responder Rate: *Positive Response Rate* was defined as satisfaction of both of the following 2 criteria:

- ≥ 25% reduction from baseline to endpoint in the ABC Irritability Subscale score;
 AND
- CGI-I scale rating of 1 (very much improved) or 2 (much improved) at study endpoint

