- 5. An individual for whom the caregiver decides not to permit participation in the study will continue to work with the physician on the ASD treatment plan goals for the minor patient.

Compensation

A subject or his or her caregiver(s) will not be offered money or any other form of compensation to participate in the clinical study; however, there will also not be any charge for the cost of the study treatments with the Erchonia® HLS laser device or for the cost of any other directly-related evaluations or measurements that occur as part of the subject's participation in this study.

Subject Sample Size

There will be 40 qualified subjects enrolled in this clinical study:

- 20 subjects in the test group
- 20 subjects in the control (placebo) group

Rationale and Justification for Sample Size

This study is powered to compare one active arm with placebo. Sample size calculation is based on the primary efficacy measure of the mean change from study baseline to endpoint (end of the 4-week treatment period) in the Aberrant Behavior Checklist (ABC) Irritability Subscale score adjusted for the baseline ABC Irritability Subscale score.

Based on detecting a mean difference of -8.5 points between test and placebo groups in the change in ABC Irritability Subscale score adjusted for the baseline ABC Irritability Subscale score being considered clinically relevant with a SD of 8.9, a two-sided test with 80% power and a 5% level of significance, the number of subjects needed per treatment group is 18.

From here, it is anticipated that about one-tenth of subjects overall may withdraw or be terminated from the study prior to completion for various reasons. Therefore, the following formula is used to determine the final needed starting sample size for each procedure arm:

Final sample size = sample size X 1/(1-d); where d = # expected dropouts/# subjects enrolled.

Final sample size = $18 \times 1/(1-0.11)$; where d = 2/19

Final sample size = 18 X 1/0.89 = 18 X 1.124 = 20 subjects per treatment group.

Therefore, a minimum starting sample size of 20 subjects in each treatment group (40 subjects in total) is needed to insure that a sufficient number remains at study endpoint (18 evaluable subjects per treatment group) for any significant differences found between treatment groups to be considered statistically valid and representative of the general population being sampled.

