CAREGIVER SATISFACTION WITH STUDY OUTCOME

The subject's caregiver is asked to rate how satisfied he or she is with any change in their child's autism symptoms and behaviors overall following completion of the laser administration procedures with the Erchonia® HLS by using the 5-point Likert scale presented below to respond to the following question:

"Overall, how satisfied or dissatisfied are you with any change in your child's autism symptoms and behaviors overall following the study procedures with the study laser device?"

- Very Satisfied
- Somewhat Satisfied
- Neither Satisfied nor Dissatisfied
- Not Very Satisfied
- Not at All Satisfied

The **Spanish Translation** of the study Caregiver Satisfaction with Study Outcome assessment tool that will be administered in this study will be performed by Language Scientific, Inc. The translated document will be supported by a notarized Certification of Translation

BLINDING EFFICACY EVALUATION TOOLS

Caregiver Perceived Group Allocation and Rationale

The caregiver records whether he or she believes that their child received the study treatment with the true or fake Erchonia® HLS and records verbatim his or her reasoning or rationale for this perceived determination.

Assessment Investigator Perceived Subject Group Allocation and Rationale

The Assessment Investigator records whether he or she believes the subject to have received the study treatment with the true or fake Erchonia® HLS™ and records verbatim his or her reasoning or rationale for this perceived determination.

The **Spanish Translation** of the study Blinding Efficacy Evaluation assessment tools that will be administered in this study will be performed by Language Scientific, Inc. The translated documents will be supported by a notarized Certification of Translation.

STUDY PROCEDURE PROTOCOL

PRE-TREATMENT ACTIVITIES

STUDY QUALIFICATION

SIGNING OF INFORMED CONSENT FORM

The PI will commence by presenting and reviewing in detail the items in the informed consent form with the individual's designated caregiver(s) and answer any questions he or she may have. To proceed, the individual's designated caregiver must willingly sign the informed consent form.

ASSIGNMENT OF SUBJECT IDENTIFICATION NUMBER

The subject will be assigned a unique subject identification number based upon his or her order of entry into the study.

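### Caregiver satisfaction, an ordered five-point secondary outcome, is compared by a Fisher's exact test that ignores the order and names no visit

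*Combined protocol and SAP*

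**What the plan says.** The Study Test Battery has the caregiver rate satisfaction with any change in the child's symptoms "by using the 5-point Likert scale presented below". The scale runs in order from Very Satisfied to Not at All Satisfied. Under Secondary Efficacy Outcome Measures the outcome is listed as "Caregiver Satisfaction with Study Outcome ratings between treatment groups and across evaluations". The Study Evaluation Timeline collects it twice, at the end of Week 4 and at Week 8, and not before Week 4.

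The only analysis text is the short Caregiver Satisfaction paragraph in the Statistical Analysis Plan. It says "Caregiver satisfaction ratings will be descriptively presented through the number and percentage of responses per response category", and then that "Fischer's Exact Test will be employed to determine the significance of the difference in categorical responses between treatment groups". It gives no visit, scores, rule for collapsing categories, or method for the comparison across evaluations.

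Nearby text is more specific. The CGI ratings go to the generalized Cochran-Mantel-Haenszel (CMH) framework, which can use order, and the blinding analysis names the study endpoint as its visit.

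**The concern.** With no collapsing rule, the paragraph is most naturally read as an exact test on a 2×5 table (the Freeman-Halton extension of Fisher's test). That test looks for any difference between the two sets of five proportions. The difference a sponsor would want to show here is one of direction: caregivers in the active arm more satisfied than those in the placebo arm. A test that ignores order spreads its power over patterns of no interest and, with about 20 per arm, has less left for that shift.

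The open visit is a second, smaller gap. With two collection times and no rule, either could be reported as the comparison between arms.

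The stakes are limited to a secondary outcome. Study success rests on the ABC Irritability analysis, and the positive-response definition does not use satisfaction.

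**Working it through.** **Sample size.** The plan gives "with a SD of 8.9, a two-sided test with 80% power and a 5% level of significance" and a difference of 8.5 points. By the normal approximation, n per arm = 2 × (1.96 + 0.84)² × (8.9/8.5)² = 2 × 7.84 × 1.096 = 17.2, rounded up to 18. This reproduces the plan's figure. The plan then takes 18/0.89 = 20.2 as 20 enrolled per arm. These figures concern the primary outcome; the plan gives no power for satisfaction. Both sizes are used below.

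**Does the test use order?** Take an illustrative table, Very Satisfied to Not at All Satisfied: active 7/6/4/2/1, placebo 2/4/6/5/3. The column totals are 9/10/10/7/4.

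- *Fisher 2×5.* Given the margins, the table's probability is the product of C(total, active) over the five columns, divided by C(40, 20). The p-value sums the probabilities of all tables no more likely than the one observed. A product does not depend on column order. Result: p = 0.244.
- *Wilcoxon.* The midranks are 5, 14.5, 24.5, 33 and 38.5. The active rank sum is 35 + 87 + 98 + 66 + 38.5 = 324.5, against 20 × 20.5 = 410 expected, a difference of −85.5. The tie-corrected variance is (20 × 20/40) × 5072/39 = 1300.5. Chi-square = 85.5²/1300.5 = 5.62 on 1 df, p = 0.018. The CMH row-mean-scores test with midrank scores is this same statistic.
- *Top two categories against the rest.* 13/20 against 6/20, Fisher p = 0.056.
- *Swap the 2nd and 4th categories in both arms.* Fisher 2×5 stays at 0.244. The active rank sum becomes 374.5, so chi-square = 35.5²/1300.5 = 0.97 and the Wilcoxon p = 0.325.

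**Power.** These inputs are assumptions, because the documents give no satisfaction distribution. Four placebo distributions (%) were used: 10/20/30/25/15, 5/10/25/30/30, 25/30/25/12/8 and 5/10/60/15/10. The active arm is shifted on a latent normal scale. There were 10,000 simulated trials per scenario, tested two-sided at 5%, with a fully enumerated Fisher p and a tie-corrected Wilcoxon without continuity correction. Ranges are over the four distributions.

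| Shift (SD) | n per arm | Fisher 2×5 | Wilcoxon | Loss (points) |
|---|---|---|---|---|
| 0 | 20 | 4.7–5.0% | 5.0–5.2% | – |
| 0.5 | 20 | 15.1–16.9% | 28.5–30.9% | 13–14 |
| 0.955 | 20 | 50.9–55.6% | 76.0–80.3% | 22–25 |
| 1.2 | 20 | 73.9–78.4% | 91.0–93.9% | 15–18 |
| 1.553 | 20 | 92.2–95.7% | 98.4–99.5% | 4–6 |
| 2.0 | 20 | 99.0–99.8% | 99.9–100% | under 1 |
| 0.5 | 18 | 13.1–15.5% | 26.1–28.6% | 12–14 |
| 0.955 | 18 | 44.3–49.4% | 71.2–74.6% | 23–27 |
| 1.553 | 18 | 89.2–92.8% | 97.1–98.9% | 6–8 |

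The null rates show that the gain does not come from a looser test.

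The anchors are 8.5/8.9 = 0.955 and 13.82/8.9 = 1.553. The second takes the earlier trial's adjusted difference ("placebo subjects was -13.82 in favor of the active procedure group") on the planning SD. On that trial's own change SDs for the test and placebo groups, the pooled SD is √((20 × 6.40² + 18 × 1.38²)/38) = 4.74, and 13.82/4.74 = 2.9 SD. That is beyond the 2.0 SD row.

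**A second model.** Proportional odds with three other placebo distributions (20/20/20/20/20, 10/20/40/20/10 and 5/10/35/30/20), 18 or 20 per arm and 2,000 trials per scenario, gave:

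- odds ratio 3: Fisher 22.5–26.6%, Wilcoxon 42.1–48.9%;
- odds ratio 5: Fisher 47.3–55.7%, Wilcoxon 72.0–79.2%.

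**If a top-two split was intended.** At 20 per arm, Fisher 2×2 has 47.6–50.7% power at 0.955 SD and 83.1–93.4% at 1.553 SD, never above the 2×5 test. At 18 per arm it beats the 2×5 test in places (52.4% against 49.2% for the first distribution at 0.955 SD), but Wilcoxon has 74.3% there.

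**Open visit.** Testing both visits at 5% gives a chance of at least one false positive between 5% (perfectly correlated results) and 1 − 0.95² = 9.75% (independent results).

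**The case against.** The strongest reply is that nothing here is wrong. Fisher's test is valid, the outcome is secondary and partly descriptive, and a general difference between arms is what the plan says it will test. An ordinal test changes the question. For a polarised pattern (assumed active 40/5/10/5/40 against placebo 10/20/40/20/10), Fisher has 92% power and Wilcoxon 7%. For a milder one (active 30/10/20/10/30, same placebo) the figures are 54% and 6%. This stands as the real cost of the change. But such a pattern shows no higher satisfaction in either arm, and the retained table of counts and percentages would reveal it.

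Second, the size of the loss is assumed, and the largest loss sits at an effect borrowed from another outcome. The sponsor's own evidence points to a much larger effect: 1.55 to 2.9 SD on irritability, depending on the SD used. In that range the loss at 20 per arm runs from 4–6 points to under 1. This also stands. However, the present trial is sized to detect 8.5 points, not 13.82, and for shifts of 0.5 to 1.2 SD the loss appears under every distribution tried.

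Third, the visit is partly covered elsewhere. The secondary outcome list refers to evaluations in the plural and the timeline names both. That is fair: what is missing is which visit leads and what the comparison across evaluations consists of. That gap would be a clarification if it stood alone.

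**Conclusion.** The concern holds. The planned test ignores the order of an ordered scale, and the analysis text names no visit. That much follows from the documents without any assumption.

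The practical loss depends on an unknown effect. With 20 per arm it is about 13–25 points of power for shifts of 0.5 to 1.2 SD, 4–6 points at 1.55 SD, and negligible from 2.0 SD upwards. These figures rest on assumed placebo distributions and a shift model.

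The fault is inefficiency and missing detail, not bias or an inflated error rate. It does not touch the primary analysis, study success or the responder rule. The change is worth making because it is nearly free.

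**What to change.** Replace the test sentence in the Caregiver Satisfaction paragraph so that it states the following.

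- The arms are compared at Week 4 with a two-sided Wilcoxon rank-sum test on the five uncollapsed categories, with Week 8 supportive. The CMH row-mean-scores test with midrank scores is equivalent, so name one of the two and say whether its p-value is exact or asymptotic. The power figures above use the asymptotic, tie-corrected form.
- Observed ratings are used at Week 4. The general rule is "if no observation was recorded at that time point, data carried forward from the previous time point with available data", but no satisfaction rating exists before Week 4 to carry forward. State also how a missing Week 8 rating is handled, since that rule would carry the Week 4 rating forward.
- Counts and percentages by arm are shown at both visits, and this table meets the listed comparison across evaluations.

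The same edit could tidy the neighbouring CGI text, as a clarification and not a further error. The outcome "Change in ratings on the CGI-I from baseline to study endpoint evaluation" has no baseline value, because only CGI-S is taken at baseline and CGI-I already rates change since then. Call it the CGI-I rating at Week 4. Name the row-mean-scores statistic with midrank scores for the CGI-I rating and the CGI-S change, and treat code 0 (not assessed) as missing.

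The cost is a few SAP lines, with the same data, visits and sample size. The one statistical price is low power for differences that are not shifts, which the retained table covers.
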